Study Design	
1- General
 
 
a. SRNAs, CRNAs, and Physicians in the anesthesiology department who normally performs IV Starts as part of patient care may participate.
 
b. Study type: Prospective, Randomized Controlled Trial
 
 
2- Clinician Training
 
Each participating clinician will watch a training video and practice on a phantom to gain proficiency with the SU-VEID device prior to study participation.
 
3- The trial
 
 
- The potential intravenous catheter inserter will assess the difficulty of the IV start preoperatively
 
- Pre-surgical subjects requiring an IV without adequate visually visible veins on the arms will be considered difficult venous access and approached for consent.
 
- Subjects who are consented/ assent will be assigned a study number and randomized to either standard IV insertion or with SU-VEID by the research assistant
 
- The clinician will perform procedures with or without SU-VEID, according to the randomization scheme. To allow analysis across all clinicians, an individual clinician's participation will be limited to no more than 50% above/below the number of subjects that would occur if the subjects were distributed equally
 
 
4- A minimum of 200 subjects per control group and 200 subjects for the Study group.
 
 
- Subjects will be stratified to 200 (100 control, 100 SU-VEID) total using near infra-red vein (NIR) visualization and 200 (100 control, 100 SU-VEID) total using ultrasound (US) vein visualization. Targeting type I/II error rates of 0.05 and 0.2, respectively, this sample size would detect improvement of first pass success from 50% to 66%.
 

Study Groups	Pediatric patients in surgical pre-op (0-18 years old), requiring an I.V. catheter for surgery who are difficult venous access.

Study Population	
Inclusion
 
 
-Patient age <math>\leq</math> 18 requiring an IV for surgery who is difficult venous access
 
-Written informed consent/ assent from the patient or legal guardian.
 
 
Exclusion
 
 
-Patient age <math>></math> 18
 
-placement of the IV will be done according to standard operating room procedures, which typically is after induction of general anesthesia by mask
 

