Number of Subjects	A total of 400 difficult venous access patients will be stratified between using either 200 NIR or 200 US vein visualization technology to achieve venous access. Within each vein visualization device group, the patients will be randomized to either standard or using SU-VEID as an adjunct for IV catheter insertion. Please see above for sample size calculation.
Study Duration	6 months
# of Clinical Sites	1
Primary End Points	IV Start first-attempt success rate increases when using the SU-VEID Device in comparison to the conventional procedure.
Secondary End Point	
 
1- Success rate of IV access within two sticks when using NIR technology.
 
2- Success rate of IV access within two sticks when using US technology.
 
3- Total procedural time required to achieve successful cannulation in comparison to conventional IV Start procedure.
 

Statistical Analysis	Paired T-test (Each clinician conducts procedures with and without the device), Chi-Squared (Measuring differences in vein difficulty pre-assessment versus control and study group success rate),
Study Sponsor	Angie Technologies Ltd.

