## **Device Description**

SU-VEID is a vein entry indicator device. The device is an electronic and algorithm-controlled pressure sensitive device, tiny, and integrated to flash chamber of an IV catheter. The device signals by beeps and lights instantly when entering the vein lumen and continues signaling as long as the tip of the needle is within the vein. After exiting the vein (either backwards or forward), once the tip of the needle re-enters the vein, the device signals again. Hence the device is an aid for venous lumen entry and alerts the clinician if the needle strays outside the lumen during the insertion process. The auditory feedback is overt, faster and more sensitive than the venous pressure/ capillary action required to see blood in the flash chamber. Moreover, the device allows the clinician to focus their vision on the insertion technology (ultrasound screen or NIR field), rather than divide it between that and the flash chamber. Therefore, it is believed that it will improve stick success.

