## SU-VEID attached but not activated

### BACKGROUND

#### **Problem worth solving**

Every year in US, hundreds of millions of IV placements are conducted. Nurses and Physicians experience the difficulties and the stresses which are involved with vascular access. Improving first attempt success is an important goal which will reduce vessel injury, pain of multiple insertions, reduces the risk of catheter related blood infections, risk of staff needle stick injuries, cost and increases patient satisfaction.

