### **Description of the SU-VEID**

The SU-VEID is a sterile disposable device for indicating a position of the needle tip relative to a blood vessel of a patient, detecting and indicating entry of an intravascular catheter into a blood vessel. The device is configured to be attached to a proximal end of the catheter so that a lumen of the catheter is in continuity with the device, and the pressure of the blood or surrounding tissues is continuously measured using a pressure sensor of the device.

The device comprises: a pressure sensor configured to produce pressure values correlative to the surrounding pressure; a signal processor; an emitter configured to produce sound and an emitter configured to produce light. The pressure sensor responds to the changes in the pressure within the needle and activates a signal by an algorithm. The signal is indicated through simultaneous activation of the sound and light emitter. Accordingly, the device enables an instant identification of penetration by an intravascular catheter of both walls of a blood vessel by means of analysis of pressures history and changes in the pressure levels. The indications are instant, enabling the clinician to react instantly to the emitters signal, thereby avoiding double puncturing (infiltration). Furthermore, the indications are correlated to the state of the tip of the needle, i.e., a different indication signal is received while the tip of the needle is within the vein than when the tip of the needle is outside the vein.

The instant response also solves the problem of double penetration, i.e., crossing the distal wall of the vein, as in the case of double penetration the signal indication will cease. The cannula then needs to be slightly pulled back in position, until the signal is obtained once again without the cannula being removed from the patient's body. This increases the probability of completing and finalizing the procedure while the cannula is properly situated inside the vein.

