### **Benefit**

Subjects may benefit by having the IV catheterization procedure performed with less attempts, easier and quicker with the SU-VEID device, therefore less exposure to risks.

Further, SU-VEID does not interfere with the normal blood return into the flash chamber of the catheter so its use does not obstruct a clinician's normal cues of entry into the vein. What it does is identify the precise time of entry into the lumen even if the patient's volume status is low and blood refill into the catheter is slow. This should allow the clinician to reduce "back wall" injury of the vessel and hence increase success.

Terms:

SU-VEID	Disposable sterile vein entry indicator device, FDA approved.
Success	The cannula is placed inside a vein and secured.
Fail	The procedure stopped due to a failure or the cannula found to be placed outside a vein right after completing the procedure, or a short time later.
IN-State	The needle's tip or the cannula's tip are inside a vein.
Sound of success	Fast beeps (8 per second) indicating in-vein Success state.
Sound of operation	Slow beeps (1 per second) indicating out of vein state
Half Detach	A temporary state while pulling the needle from a cannula or sliding forward the cannula on the needle for about an inch, the clinician normally ceases the detachment for a moment and hold (to see the blood upward in cannula) while the needle is still partially inside the cannula.
Full Detach	A state, where the needle is fully pulled out from the cannula.
AT	Angie Technologies Ltd.
SPIV	Short Peripheral Intravenous
DVA/DIVA	Difficult Intravenous Access

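### Does the missing start event for procedural time (secondary endpoint 3) leave the time comparison open to bias between arms?

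*Combined protocol and SAP*

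**What the plan says.** Procedural time appears as an endpoint once, in the synopsis under Secondary End Point, item 3: "Total procedural time required to achieve successful cannulation in comparison to conventional IV Start procedure". No start event, list of included steps or expected value is attached to it.

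Other parts of the document bear on how it would be read:

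- **Stop event.** The Terms table defines Success as "The cannula is placed inside a vein and secured". Fail includes the case of "the cannula found to be placed outside a vein right after completing the procedure, or a short time later".
- **Device preparation.** Description of the SU-VEID says "The device is configured to be attached to a proximal end of the catheter". A line just before Background, apparently the caption of a figure not reproduced in the text, reads "SU-VEID attached but not activated". Against this, the synopsis (Study Device) and Device Description both call the device integrated with the catheter.
- **Device signal.** The Terms table describes the sound of success as "Fast beeps (8 per second) indicating in-vein Success state". Slow beeps mark the out-of-vein state, so the device is already running before vein entry.
- **Control arm.** This is standard IV insertion; no inactive device is described.
- **Population.** Patients are those "requiring an IV for surgery who is difficult venous access", so eventual cannulation is the expected outcome for all.
- **Tests.** Statistical Analysis lists a paired t-test by clinician and a chi-squared test, the latter tied to success rates.

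**The concern.** A duration needs two ends, and the plan names at most one. The missing end is not neutral between arms. Any attachment or activation happens only with SU-VEID, so a clock that starts before the device is ready charges that arm for preparation, and a clock that starts at skin puncture does not. Two analysts could report different time benefits from the same procedures. The beeps reveal the arm and no blinding of the timekeeper is described, so the choice could be made with the arm known.

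The endpoint has some weight. The Benefit section expects a quicker procedure, Device Description says "The auditory feedback is overt, faster and more sensitive", and this is the only endpoint that tests speed. Related details are also unwritten: whether intervals between sticks count, how a cannula later found outside the vein is timed, and whether the in-vein beep could be taken as the stop.

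**Working it through.** **Is there a figure to reproduce?** No. The documents give no expected time, standard deviation (SD), difference or power for this endpoint. The only planning figures are for first-pass success: 50% against 66%, with 200 per arm in total.

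**What follows without assumptions.** Suppose setup takes s seconds, once per patient, in the SU-VEID arm only. Counting it raises that arm's mean, and so the difference (device minus control), by exactly s. The same holds for each clinician's mean difference in a paired analysis. The direction is certain; the size is not, because s is not given.

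**Illustration.** From the plan: 50% and 66%, 200 per arm. Assumed: the same success probability at every stick, independent sticks, everyone timed to cannulation, and stick time log-normal with median 60 s and log SD 0.4.

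- Mean per stick: 60 × exp(0.4²/2) = 65.0 s.
- Mean sticks to success: 1/0.50 = 2.000 and 1/0.66 = 1.515.
- Difference without setup or intervals: 65.0 × (1.515 − 2.000) = −31.5 s.
- Intervals of 60 s between sticks, if counted, add 60 × (0.515 − 1.000) = −29.1 s, for a total of −60.6 s.

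| Setup, once per patient | Intervals not counted | 60 s intervals counted |
|---|---|---|
| 0 s | −31.5 s (power 97%) | −60.6 s (98%) |
| 5 s | −26.5 s (90%) | −55.6 s (96%) |
| 10 s | −21.5 s (73%) | −50.6 s (92%) |
| 20 s | −11.5 s (27%) | −40.6 s (77%) |

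Power is simulated for a two-sided 5% unequal-variance t-test on patients, a stand-in for the listed paired test. A rough check of the 20 s entry without intervals: the within-arm SDs are about 100 and 66 s, so the standard error is √(100²/200 + 66²/200) = 8.5 s. The ratio 11.5/8.5 is about 1.36, which gives power near 27%.

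**Sensitivity to the base rate.** The table assumes 2.0 control sticks on average. The Clinical Benchmark section gives three or more attempts in difficult-access patients. Taking exactly three means success of 1/3 per stick; the same 16-point gain gives 0.333 + 0.160 = 0.493, or 2.027 sticks. The difference is then 65.0 × (2.027 − 3.000) = −63.2 s. With 20 s of setup and intervals not counted it is −43.2 s, with simulated power of about 91% in place of 27%. The striking entries in the table therefore depend on inputs that the documents do not fix.

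**How much the text already settles.**

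| Question | What the document offers |
|---|---|
| Stop | Success is defined as placed and secured. The beep is a separate entry in the same table, so it is not the stop. |
| Intervals between sticks | The endpoint is total time to successful cannulation, which favours counting them. |
| Never cannulated | Every patient needs the line for surgery; nothing suggests that a material share go without. |
| Test | Time is the only continuous endpoint, and the paired t-test is the only listed test for a continuous outcome. |
| Start, and whether setup counts | Not stated. |

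The start remains open, along with the minor matter of how to time a cannula found misplaced later.

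**The case for a change.** The strongest case for a change is that a start time not recorded during the procedure cannot be reliably recovered afterwards, so the rule has to be in place before enrolment. It would cost a few lines and a few time stamps. The device is described both as attached and as integrated, so the documents do not show that setup is negligible. With 20 to 30 s of setup, the illustration moves from a clear benefit to almost none (at 30 s, −31.5 + 30 = −1.5 s).

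Part of this stands. The start is unwritten, and a one-arm setup step would move the result in a known direction. The procedure record does need a start time that means the same in both arms. That is ordinary data-collection detail, however, and nothing the plan states would produce a wrong answer. Including preparation and excluding it are both defensible definitions; they differ by the setup time itself, which can be observed and reported. The large effects need setup times that no section describes, combined with a low assumed number of control attempts.

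A longer set of rules would bring problems of its own. Ranking uncannulated patients longest does not fit a comparison of means. Saying that a misplaced cannula does not stop the clock, while adding only later procedure time, is inconsistent. Nothing shows that an adjusted mean difference would serve better than the listed paired test.

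**Conclusion.** The observation is correct, but no change to the plan is needed. Secondary endpoint 3 lacks a stated start and does not say whether device preparation counts. The stop, the treatment of intervals and the applicable test can be read from the document. An analyst would fill the remaining gap with one start event applied to both arms, and could show time from first skin puncture beside it.

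The size of the effect cannot be derived from the documents: it equals the setup time, once per patient or once per stick. If the device comes attached and activation takes a few seconds, it is small. At 10 s it removes 10 of 31.5 s in the illustration with 2.0 control sticks, and 10 of 63.2 s in the one with three. Both rest on an assumed 65 s per stick and independent sticks. The primary endpoint, the sample size and the within-two-sticks endpoints do not use procedural time and are unaffected.

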Use of SU-VEID™ As An Adjunct to Vein  
Visualization Technology to Improve Peripheral  
Venous Access Success in Children

NCT05204082

September 15, 2021

[figure not shown]
**Use of SU-VEID as an adjunct to vein visualization technology to improve peripheral venous access success in difficult venous access patients**

[figure not shown]
Title	Use of SU-VEID as an adjunct to vein visualization technology to improve peripheral venous access success in children
Study Number	1.0
Study Objectives	Intravenous access is often technically difficult in children because of the small diameter, inability to feel or see the veins. We propose to determine if use of the SU-VEID™ in children facilitates an increase success rate of peripheral intravenous starts, in comparison to conventional vein entry techniques.
Study Device	SU-VEID Single Use Vein Entry Indicator Device.  Electronic pressure sensing device, integrated to a conventional needle catheter, and which indicates continuously during intravenous cannulation: whether the tip of the needle is inside or outside of a vein, to assist a clinician in intravenous cannulation.
Indication for Use	The SU-VEID is used to indicate the location of the vein (in relation to a tip of a needle): including indication of vein entry, vein double puncture (infiltration), vein re-entry and vein exit of an intravenous catheter system's needle.

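### Children aged 0-18 are analysed together and neither listed analysis uses age; pre-specifying an age term in a patient-level model is a cheap efficiency gain of uncertain, probably small, size

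*Combined protocol and SAP*

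**What the plan says.** All of this is in the synopsis table of the combined protocol and SAP.

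- **Study Groups** describes one population: "Pediatric patients in surgical pre-op (0-18 years old"), with difficult venous access. No age strata or age subgroups appear anywhere.
- **Study Objectives** says that access is often "technically difficult in children because of the small diameter", and in the same sentence adds veins that cannot be felt or seen. Age itself is not named as a predictor.
- **Study Design** approaches for consent only children whose arm veins are not adequately visible. Together with **Number of Subjects**, it describes randomisation within the NIR and US groups and no other stratification factor.
- **Primary End Points** is "IV Start first-attempt success rate increases when using the SU-VEID Device in comparison to the conventional procedure".
- **Statistical Analysis** lists two methods: "Paired T-test (Each clinician conducts procedures with and without the device"), and a chi-squared test relating pre-assessed vein difficulty to success by group. The row does not assign either method to an endpoint. The paired t-test reads as the device comparison, with the clinician as the pairing unit.

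**The concern.** If small veins cause failed attempts, age is a natural baseline proxy for vein size over a range from birth to 18 years. It must be known for every child, because it decides eligibility. A paired t-test by clinician reduces the data to one average per clinician per arm, so a patient's age cannot enter it. The chi-squared test concerns assessed difficulty, not age. Age is not balanced by design either.

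What is at stake is efficiency. Any outcome variation explained by age stays in the error term, and a chance difference in age between arms adds noise to the realised estimate. Without a pre-specified age term, a visible age imbalance would also invite a post-hoc argument over adjustment.

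**Working it through.** **1. The plan's own figure.** Study Design gives "Targeting type I/II error rates of 0.05 and 0.2, respectively", and says "this sample size would detect improvement of first pass success from 50% to 66" per cent. Sidedness is not stated; I take two-sided. For two proportions with pooled variance under the null:

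n per arm = [1.96 × √(2 × 0.58 × 0.42) + 0.8416 × √(0.50 × 0.50 + 0.66 × 0.34)]² / 0.16² = (1.368 + 0.580)² / 0.0256 = 148.2, so 149.

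One-sided it is 117. Neither matches 100 per arm (each technology group) or 200 per arm (overall). Two-sided power is 63.2% at 100 and 90.3% at 200. That mismatch is a separate matter. Here it only sets the baseline: about 90% unadjusted power overall, from "A minimum of 200 subjects per control group and 200 subjects for the Study group".

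**2. Assumed age gradients.** The documents give no success rate by age and no age distribution. I assume age uniform on 0-18 (SD 18/√12 = 5.20 years) and log-odds of success linear in age, centred on 50% in controls.

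| Control success, age 0 to 18 | OR per SD of age | Outcome variance explained (R²) |
|---|---|---|
| 40% to 60% | 1.26 | 1.3% |
| 30% to 70% | 1.63 | 5.6% |
| 20% to 80% | 2.23 | 13.4% |

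For example, 20% to 80% is 2 × ln(4) = 2.77 on the log-odds scale over 18 years. That is 2.77 × 5.20/18 = 0.80 per SD, or OR 2.23.

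**3. Power gain at 50% v 66%, 200 per arm.** Simulation used 4,000 trials per setting, comparing an unadjusted two-proportion z-test with a logistic model containing arm and linear age. The approximation replaces n by n/(1 − R²) in the power formula, for example 200/(1 − 0.134) = 231, starting from 90.3%.

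| Gradient | Simulated, unadjusted → adjusted | Gain (points) | Approximation, adjusted |
|---|---|---|---|
| 40-60% | 89.5% → 89.9% | 0.4 | 90.7% |
| 30-70% | 89.6% → 91.4% | 1.8 | 91.8% |
| 20-80% | 90.2% → 94.0% | 3.8 | 93.9% |

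Simulation error is about 0.5 point, so the first gain cannot be told from zero. Rejection rates under the null were 0.046 to 0.049, with patients independent.

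**4. Separate simulation by OR per SD of age (unadjusted → adjusted).**

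| OR per SD | 200 per arm | 100 per arm |
|---|---|---|
| 1.0 | 89.6% → 89.7% | 63.4% → 62.5% |
| 1.25 | 90.0% → 90.4% | 63.0% → 62.8% |
| 1.5 | 90.6% → 91.3% | 65.4% → 65.4% |
| 2.0 | 89.9% → 92.7% | 66.0% → 69.4% |
| 3.0 | 90.1% → 95.2% | 64.9% → 73.6% |

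OR 3 is steeper than the 20-80% gradient. The largest loss, 0.9 point at 100 per arm when age has no effect, is close to the simulation error there of about 0.8 point.

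**5. Against the planned test.** Steps 3 and 4 isolate age by comparing two patient-level analyses; the z-test is not in the plan. To compare with the paired t-test, the number of clinicians must be assumed. With 20 clinicians, 10 patients per arm each, no clinician variation in the device effect and no age effect, the standard error is √(0.4744/10)/√20 = 0.0487. The non-centrality is then 0.16/0.0487 = 3.29 against a critical value of 2.09 on 19 degrees of freedom, giving power of about 0.88. Simulation with 20 clinicians gave about 0.84-0.87 for the paired t-test and about 0.90-0.93 for a patient-level logistic model with clinician, technology and age. Of that difference, age contributed nothing to about 4 points; the rest comes from working per patient. Type I error stayed near 0.05, but rose to about 0.07 with 20 clinician dummies at the steepest gradient, which favours a random effect.

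**6. Chance imbalance.** The SD of the between-arm difference in mean age is 5.20 × √(2/200) = 0.52 years. At average slopes of 20/18, 40/18 and 60/18 points per year, a 1-SD imbalance moves the estimated difference by about 0.6, 1.2 or 1.7 points. The standard error of that difference is √(0.4744/200) = 4.9 points.

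**7. Effect measure.** With an age term, the logistic coefficient is a conditional odds ratio: 1.99, 2.09 and 2.33 at OR per SD 1.5, 2 and 3, against a marginal 0.66 × 0.50/(0.34 × 0.50) = 1.94. Standardising to a difference in success rates keeps the marginal quantity on which the sample size is based.

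**The case against.** **Age may predict little here.** The rationale names veins that cannot be felt or seen as well as small diameter, and every enrolled child lacks adequately visible arm veins. An older child who qualifies is already a hard case, so the gradient may be flatter than in children generally. This stands, and it is why no single gain can be promised. It does not remove the case, because selecting on visibility does not fix vein diameter.

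**A reader might infer bias, or that chance age imbalance undermines the result.** The documents do not support that. Allocation is randomised, the unadjusted comparison is unbiased, and chance imbalance is random error that the test and interval already cover. Step 6 shows that it is small beside the standard error.

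**A reader might infer that adjustment would certainly add power at no cost.** That is not supported either. The documents give no age gradient, and a paired t-test cannot accept the covariate, so the primary method has to be replaced.

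**The plan is built around clinicians.** It pairs by clinician and caps each clinician's share of subjects so that results can be analysed across clinicians. An age-adjusted model without a clinician term would discard this. That objection is right, so clinician belongs in the model.

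**Pre-assessed difficulty may be the closer covariate.** Possibly. The documents do not give its scale, and they do not show whether age adds anything beyond it.

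**Conclusion.** The point holds as an efficiency improvement, not as an error in the plan. The documents confirm that ages 0-18 are pooled, that small diameter is named as a cause of difficulty, that randomisation is within NIR/US only, and that neither listed analysis uses age. The gain from age is roughly 0 to 4 points of power at 200 per arm and 50% v 66%, for control gradients from 40-60% to 20-80%. At 100 per arm, in line with "Subjects will be stratified to 200 (100 control, 100 SU-VEID) total using near infra-red vein (NIR) visualization", there is no gain up to OR 1.5 per SD and about 3 points at OR 2. These figures rest on uniform ages, a log-odds gradient linear in age and a two-sided 0.05 test, none of which the documents state. The comparison with the paired t-test also rests on an assumed 20 clinicians. In the same row, the mismatch between a clinician-paired t-test and a patient-level two-proportion sample size matters more than age, and one change can address both.

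**What to change.** In the Statistical Analysis row, replace the paired t-test as the primary analysis with a pre-specified patient-level logistic model for first-attempt success. It should contain arm, technology group (NIR/US), clinician (for example as a random effect) and age in a form fixed in advance (for example log age or a spline). Report the standardised difference in success rates with a 95% CI. Use the same age and clinician terms for two-stick success and for procedural time, each in a model suited to that outcome.

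Cost: a short amendment to one row, and no new measurement as long as the age used for eligibility is recorded. The primary method changes, and both the form of age and the effect measure must be fixed before outcome data are seen. If age proves weakly prognostic, the gain is negligible, with little or no loss of power.

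### Patients are randomised within NIR and US groups, but neither listed analysis is described as using those groups for first-attempt success; the cost is a mildly conservative test and a small loss of power, not bias.

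*Combined protocol and SAP*

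**What the plan says.** The Study Design row (item 4) sets the group sizes: "Subjects will be stratified to 200 (100 control, 100 SU-VEID) total using near infra-red vein (NIR) visualization", with the same numbers for US. The Number of Subjects row adds: "Within each vein visualization device group, the patients will be randomized to either standard or using SU-VEID as an adjunct for IV catheter insertion". The sample-size statement, with type I and II error rates of 0.05 and 0.2, is that "this sample size would detect improvement of first pass success from 50% to 66" per cent.

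The primary endpoint is "IV Start first-attempt success rate increases when using the SU-VEID Device in comparison to the conventional procedure". It does not mention visualisation technology. NIR and US appear only in secondary endpoints 1 and 2, which concern two sticks, for example "Success rate of IV access within two sticks when using NIR technology".

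The analysis is a single row with two entries: "Paired T-test (Each clinician conducts procedures with and without the device") and "Chi-Squared (Measuring differences in vein difficulty pre-assessment versus control and study group success rate"). Neither entry mentions NIR or US, and neither is tied to a named endpoint. The Study Design row also limits how far each clinician's share of patients may depart from equal, with the stated purpose "To allow analysis across all clinicians".

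**The concern.** An analysis should normally reflect the groups within which patients were randomised. Here the design pays for two balanced groups, and the analysis row does not use them for the primary endpoint.

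If NIR and US differ in first-attempt success, a comparison that ignores the groups leaves that difference in its standard error. The confidence interval is then wider than it need be, the true type I error falls below 5%, and some power is lost. The arm effect on first-attempt success within each technology would also go unreported, because the only technology-specific endpoints use two-stick success.

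**Working it through.** **Inputs.** From the Study Design row: 100 per arm in each group, 200 per arm overall, success 50% v 66%, alpha 0.05, power 80%. Assumed: two-sided testing (the plan does not say), and NIR/US control rates placed evenly around the plan's single control rate of 50%.

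**The plan's own figure.** n per arm = [1.96√(2 × 0.58 × 0.42) + 0.842√(0.50 × 0.50 + 0.66 × 0.34)]² / 0.16² = (1.368 + 0.580)² / 0.0256, which gives 149. So 200 per arm is not reproduced: it gives 90.3% power for 50% v 66%, and 100 per arm gives 63.2%. That is a separate matter. It matters here only because the two-arm comparison starts from about 90% power.

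**Where the loss comes from.** With equal group sizes and a constant risk difference, pooled variance = mean within-group variance + (gap/2)². For a 16-point effect, the average rate over the two arms is 0.58:
- 20-point gap (control 40%/60%): 0.58 × 0.42 = 0.2436; mean of 0.48 × 0.52 and 0.68 × 0.32 = 0.2336; excess 0.01 = (0.20/2)².
- 40-point gap (control 30%/70%): mean of 0.38 × 0.62 and 0.78 × 0.22 = 0.2036; excess 0.04 = (0.40/2)².

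**Bias and type I error.** With 100 per arm in each group, the pooled risk difference equals the average of the two within-group differences, so the estimate is the same with or without the groups. Under no effect and a 40-point gap, the unstratified test uses SE √(0.25 × 2/200) = 0.0500, while the true SE is √(0.21 × 2/200) = 0.0458. Its effective cut-off is 1.96 × 0.0500/0.0458 = 2.14, a type I error of about 0.033.

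**Power by simulation** (400,000 trials per setting, no continuity correction, no clinician effect; unstratified v CMH by NIR/US). The odds ratio is (0.66/0.34)/(0.50/0.50) = 1.94.

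| Control NIR/US | Null rejection | Power, constant +16 points | Power, constant odds ratio 1.94 |
|---|---|---|---|
| 50/50 | 0.051 v 0.051 | 90.0% v 90.0% | 90.0% v 90.0% |
| 40/60 | 0.046 v 0.048 | 90.6% v 91.5% | 88.2% v 89.1% |
| 35/65 | 0.041 v 0.051 | 91.2% v 92.9% | 85.6% v 87.8% |
| 30/70 | 0.033 v 0.050 | 92.1% v 94.8% | 80.7% v 85.3% |

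At +16 points the 95% CI half-width, unstratified v stratified, is 9.5 v 9.3 points at 40/60 and 9.5 v 8.7 at 30/70. For a true difference of 13.8 points, where power is near 80%, the comparison is 80.1% v 81.3% at a 20-point gap and 81.8% v 86.6% at a 40-point gap.

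**The listed paired t-test** (assumed 10 clinicians, no clinician effect). Null rejection at gaps of 0, 20 and 40 points:
- technology and arm fall to clinicians by chance: 0.049, 0.047, 0.036;
- every clinician has equal numbers in each technology and arm: 0.050, 0.050, 0.051;
- each clinician uses one technology: 0.050 throughout.

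So this test is affected only when the technology mix differs between a clinician's two arms.

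**Clinician differences.** With an assumed 10 clinicians, clinician logit SD 1, equal NIR/US rates and arms balanced within clinician, CMH by NIR/US alone has null rejection 0.034 and power 79.5%. The unstratified test coincides with it at equal rates. Adding clinician to the strata gives 0.051 and 84.4%.

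**The case against.** The strongest reply is that the power table prices a test the plan does not list. The row names a clinician-paired t-test and a chi-squared worded around vein difficulty, and neither is plainly a two-arm comparison of first-attempt success. That stands. A reader might infer that a pooled chi-squared is the planned primary test, but the row does not say so. The table shows what ignoring the groups costs in the simplest comparison, not what the plan is known to lose. What the text does support is narrower: no listed analysis is described as using the groups for this endpoint.

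Second, the gaps are assumed. That also stands. The documents give one control rate and none by technology, and at equal rates nothing is lost.

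Third, clinician differences may matter more than technology, and the design provides for analysis across clinicians. This stands and shapes the remedy. With an assumed 20 clinicians, logit SD 1 and equal NIR/US rates, the paired t-test has 80.4% power and size 0.050, against 79.1% and 0.032 for CMH by NIR/US alone. With 10 clinicians the order reverses: 74.7% v 79.5%. An NIR/US-only CMH test is therefore not shown to improve on the listed paired test.

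Fourth, the wider gap may be that no primary test is identified, and a one-line row does not exclude analysis by technology. That is fair, but naming a primary test would not by itself bring in the randomisation groups.

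**Conclusion.** The point holds and is minor. The plan randomises within NIR and US but describes no use of those groups in analysing first-attempt success. If the two technologies differ, an arm comparison that ignores them is mildly conservative. Against CMH by NIR/US, an unstratified two-arm test loses nothing at equal rates, about 1 power point at a 20-point gap and about 3 to 5 at a 40-point gap.

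These sizes assume two-sided 5% testing, 100 per arm in each group and no clinician differences. Power for the planned effect stays above 80% only if clinicians do not differ much; it is 79.5% in the 10-clinician setting above, with equal NIR/US rates.

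A reader might also infer bias or excess false positives. Neither follows: the risk difference is unbiased provided the 100/100 split is achieved in each group, and the type I error falls rather than rises. The proviso is needed because the plan states its arm sizes as minimums and names no blocking method.

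**What to change.** In the Statistical Analysis row, make the primary arm comparison of first-attempt success a Cochran-Mantel-Haenszel test stratified by NIR/US group as randomised and by clinician, with the common risk difference and its 95% CI. Report the arm effect within NIR and within US as supportive. This keeps the planned analysis across clinicians inside the primary test instead of demoting it.

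In 18 simulated settings with equal numbers per clinician, technology and arm, this test kept its size near 0.05. Its power was at least equal to that of the other tests, within simulation error.

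The cost is slightly more analysis work, with no extra patients or procedures. One limit should be accepted in advance: NIR/US-by-clinician strata with patients in only one arm contribute nothing.
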